### **5.4.3 Storage and destruction of pharmacokinetic samples**

There will be no PK study.

## **5.5 Pharmacodynamics**

### **5.5.1 Collection of samples**

Pharmacodynamic samples will not be taken during the study.

## **5.5.2 Storage, re-use and destruction of pharmacodynamic samples**

There will be no PD study.

## **5.6 Pharmacogenetics**

Pharmacogenetic samples will not be taken during the study.

### **5.6.1 Collection of pharmacogenetic samples**

### **5.6.2 Storage, re-use and destruction of pharmacogenetic samples**

## **5.7 Biomarker analysis**

The subject's consent to the use of donated biological samples is mandatory.

Additional plasma will be stored at -80 degree and may be analysed for exploratory biomarkers to assess correlations with disease activity, effects of study drug, clinical outcomes and toxicity.

### **5.7.1 Storage, re-use and destruction of biological samples**

Samples will be stored for a maximum of 15 years from the date of the Last Subject's Last Visit, after which they will be destroyed. The results of this biomarker research will be reported either in the Clinical Study Report itself or as an addendum, or separately in a scientific report or publication. The results of this biomarker research may be pooled with biomarker data from other studies with the study drug to generate hypotheses to be tested in future research.

### **5.7.2 Labelling and shipment of biological samples**

The Principal Investigator ensures that samples are labelled and shipped in accordance with the Laboratory Manual, see Appendix B International Airline Transportation Association (IATA) 6.2 Guidance Document.

### **5.7.3 Chain of custody of biological samples**

A full chain of custody is maintained for all samples throughout their lifecycle.

The Principal Investigator will keep full traceability of collected biological samples from the subjects while in storage at the centre until shipment or disposal (where appropriate) and keeps documentation of receipt of arrival.

The sample receiver keeps full traceability of the samples while in storage and during use until used or disposed of or until further shipment and keeps documentation of receipt of arrival.

Sponsor keeps oversight of the entire life cycle through internal procedures, monitoring of study sites and auditing of external laboratory providers.

#### **5.7.4 Withdrawal of Informed Consent for donated biological samples**

If a subject withdraws consent to the use of donated biological samples, the samples will be disposed of/destroyed, and the action documented. If samples are already analysed, Sponsor is not obliged to destroy the results of this research.

As collection of the biological samples is an optional part of the study, then the subject may continue in the study.

The Principal Investigator:

- Ensures subjects' withdrawal of informed consent to the use of donated samples is notified immediately to Sponsor
- Ensures that biological samples from that subject, if stored at the study site, are immediately identified, disposed of /destroyed, and the action documented
- Ensures the laboratory(ies) holding the samples is/are informed about the withdrawn consent immediately and that samples are disposed of/destroyed, the action documented and the signed document returned to the study site
- Ensures that the subject and Sponsor are informed about the sample disposal.

### **6. SAFETY REPORTING AND MEDICAL MANAGEMENT**

The Principal Investigator is responsible for ensuring that all staff involved in the study are familiar with the content of this section.

#### **6.1 Definition of adverse events**

An adverse event is the development of an undesirable medical condition or the deterioration of a pre-existing medical condition following or during exposure to a pharmaceutical product, whether or not considered causally related to the product. An undesirable medical condition can be symptoms (e.g., nausea, chest pain), signs (e.g., tachycardia, enlarged liver) or the abnormal results of an investigation (e.g., laboratory findings, electrocardiogram). In clinical studies, an AE can include an undesirable medical condition occurring at any time, including run-in or washout periods, even if no study treatment has been administered.

The term AE is used to include both serious and non-serious AEs.

#### **6.2 Definitions of serious adverse event**

A serious adverse event is an AE occurring during any study phase (i.e., run-in, treatment, washout, follow-up), that fulfils one or more of the following criteria:

- Results in death
- Is immediately life-threatening
- Requires in-patient hospitalization or prolongation of existing hospitalisation
- Results in persistent or significant disability/incapacity or substantial disruption of the ability to conduct normal life functions
- Is a congenital abnormality or birth defect
- Is an important medical event that may jeopardise the subject or may require medical intervention to prevent one of the outcomes listed above.

The causality of SAEs (their relationship to all study treatment/procedures) will be assessed by the Investigator(s) and communicated to the Independent Safety Monitor for review and to the funding agent, AstraZeneca, to support post-marketing safety surveillance data..

For further guidance on the definition of a SAE, see Appendix A Additional Safety Information to the Clinical Study Protocol.

### **6.3 Recording of adverse events**

#### **6.3.1 Time period for collection of adverse events**

Adverse Events including serious and non-serious will be collected from the time of informed consent signature throughout the treatment period of 1 year, visit 6, or last contact.

SAEs will be recorded from the time of informed consent throughout the treatment period and including the follow-up period.

#### **6.3.2 Follow-up of unresolved adverse events**

Any AEs that are unresolved at the subject's last AE assessment or other assessment/visit as appropriate in the study are followed up by the Investigator for as long as medically indicated, but without further recording in the CRF.

Company retains the right to request additional information for any subject with ongoing AE(s)/SAE(s) at the end of the study, if judged necessary.

#### **6.3.3 Variables**

The following variables will be collect for each AE;

- AE (verbatim)
- The date when the AE started and stopped
- Maximum intensity or intensity or changes in intensity

- CTCAE grade/max CTCAE grade/changes in CTCAE grade
- Whether the AE is serious or not
- Investigator causality rating against the Investigational Product (yes or no)
- Action taken with regard to investigational product
- AE caused subject's withdrawal from study (yes or no)
- Outcome.

In addition, the following variables will be collected for SAEs:

- Date AE met criteria for serious AE
- Date Investigator became aware of serious AE
- AE is serious due to
- Date of hospitalisation
- Date of discharge
- Probable cause of death
- Date of death
- Autopsy performed
- Causality assessment in relation to Study procedure(s)
- Causality assessment in relation to the investigational product
- Causality assessment in relation to Other medication
- Causality assessment in relation to Additional Study Drug
- Description of SAE.

It is important to distinguish between serious and severe AEs. Severity is a measure of intensity whereas seriousness is defined by the criteria in Section 6.2. An AE of severe intensity need not necessarily be considered serious. For example, nausea that persists for several hours may be considered severe nausea, but not a SAE unless it meets the criteria shown in Section 6.2. On the other hand, a stroke that results in only a limited degree of

disability may be considered a mild stroke but would be a SAE when it satisfies the criteria shown in Section 6.2.

#### **6.3.4 Causality collection**

The Investigator will assess causal relationship between Investigational Product and each Adverse Event, and answer ‘yes’ or ‘no’ to the question ‘Do you consider that there is a reasonable possibility that the event may have been caused by the investigational product?’

For SAEs causal relationship will also be assessed for other medication and study procedures. Note that for SAEs that could be associated with any study procedure the causal relationship is implied as ‘yes’.

The causality of AEs/SAEs as assessed by the Investigator(s) will be communicated to the Independent Safety Monitor for secondary review.

#### **6.3.5 Adverse events based on signs and symptoms**

All AEs spontaneously reported by the subject or reported in response to the open question from the study personnel: Have you had any health problems since the previous visit/you were last asked, or revealed by observation will be collected and recorded in the tool that the study personnel will be using.

When collecting AEs, the recording of diagnoses is preferred (when possible) to recording a list of signs and symptoms. However, if a diagnosis is known and there are other signs or symptoms that are not generally part of the diagnosis, the diagnosis and each sign or symptom will be recorded separately.

#### **6.3.6 Adverse events based on examinations and tests**

The results from protocol mandated laboratory tests and vital signs will be summarised in the clinical study report. Deterioration as compared to baseline in protocol-mandated glucose levels, HbA1C, liver and renal functions should therefore only be reported as AEs if they fulfil any of the SAE criteria or are the reason for discontinuation of treatment with the investigational product.

If deterioration in a laboratory value/vital sign is associated with clinical signs and symptoms, the sign or symptom will be reported as an AE and the associated laboratory result/vital sign will be considered as additional information. Wherever possible the reporting Investigator uses the clinical, rather than the laboratory term (e.g., anaemia versus low haemoglobin value). In the absence of clinical signs or symptoms, clinically relevant deteriorations in non-mandated parameters should be reported as AE(s).

Any new or aggravated clinically relevant abnormal medical finding at a physical examination as compared with the baseline assessment will be reported as an AE.

### **6.3.7 Hy's Law**

Cases where a patient shows elevations in liver biochemistry may require further evaluation and occurrences of AST or ALT  $\geq 3 \times$  ULN together with total bilirubin  $\geq 2 \times$  ULN may need to be reported as SAEs. Reporting of serious adverse events to the IRB and/or the Regulatory Authority

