## 5.2 Laboratory assessments

### 5.2.1 Laboratory assessments

The following laboratory variables will be measured. Fasting glucose, creatinine, and HbA1C will be measured at every 3 months and other variables will be assessed at every 6 months.

**Table 2** Laboratory Variables

Whole blood	Clinical Chemistry (serum or plasma)
HbA1C	S/P-Creatinine
	S/P-Fasting glucose
Clinical Chemistry (serum or plasma)	S/P-Alkaline phosphatase (ALP)
S/P-Total cholesterol	S/P-Aspartate transaminase (AST)
S/P-Triglycerides	S/P-Alanine transaminase (ALT)
S/P-LDL cholesterol	S/P-Albumin
S/P-HDL cholesterol	S/P-Potassium
S/P-Total cholesterol	S/P-Calcium, total
S/P-Creatine kinase (CK)	S/P-Sodium
S/P-ProBNP	S/P-HsCRP
S/P-Uric acid	Urinalysis
S/P-Potassium	Pregnancy test

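### The Hy's Law criterion needs total bilirubin, which the laboratory table omits, so the scheduled laboratory data cannot evaluate it

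*Combined protocol and SAP*

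**What the plan says.** Section 6.3.7 (Hy's Law) says that raised liver biochemistry "may require further evaluation and occurrences of AST or ALT" at or above 3 times ULN, in combination with total bilirubin at or above 2 times ULN, "ULN may need to be reported as SAEs". The two components are linked by "ULN together with total bilirubin", so neither is enough alone.

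Section 5.2.1 introduces Table 2 with "The following laboratory variables will be measured" and sets the timing: "Fasting glucose, creatinine, and HbA1C will be measured at every 3 months and other variables will be assessed at every 6 months". AST, ALT and ALP are in the table and fall in the six-monthly group. Total bilirubin is not in the table.

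Table 1 in section 4 has one general row for haematology and clinical chemistry samples and names no analytes. Section 6.3.6 speaks of liver function in general terms and names no analytes either.

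**The concern.** A safety rule with two required components should be supported by a measurement plan that collects both. Here one is collected and the other is not.

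Three features of this protocol make the gap matter:

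- Under section 6.3.6, a worsening of protocol-mandated liver function counts as an adverse event only if it meets a seriousness criterion or is the reason for stopping study drug. A symptom-free transaminase rise in a subject who stays on treatment is therefore not an adverse event by default. Section 6.3.7 holds the protocol's only liver-specific laboratory threshold for possible SAE reporting.
- Sections 6.9 and 6.9.2 provide no data monitoring committee. Safety review rests on the Independent Safety Monitor, whose quarterly report (section 9.2) contains what was collected in the interval. An analyte that was not collected will not be in it.
- Section 3.2 excludes severe hepatic impairment (Child-Pugh class C) and active hepatitis B or C. Milder liver disease is not excluded by name.

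At stake is whether a case that meets the protocol's own criterion would be recognised as one.

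**Working it through.** The plan gives no figure to reproduce on this point. The check is a count of Table 2 and a comparison of the relevant sections.

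**Step 1: contents of Table 2 (section 5.2.1).** The entries are HbA1C; creatinine; fasting glucose; ALP; AST; ALT; albumin; total cholesterol (twice); triglycerides; LDL cholesterol; HDL cholesterol; CK; proBNP; uric acid; potassium (twice); total calcium; sodium; hsCRP; and, under the urinalysis heading, a pregnancy test.

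- Entries: 21
- Repeats: 2 (total cholesterol, potassium)
- Distinct entries: 21 − 2 = 19
- Bilirubin entries: 0

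**Step 2: criterion against measurements.**

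| Component in 6.3.7 | In Table 2? | Scheduled timing |
|---|---|---|
| AST or ALT ≥ 3 × ULN | Yes, both | Every 6 months |
| Total bilirubin ≥ 2 × ULN | No | None |

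The criterion needs both rows to be true. With the second never observed on schedule, scheduled data can show that a subject does not meet it (both transaminases below the limit) but can never show that a subject does.

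**Step 3: search for another source.** Bilirubin is mentioned only in section 6.3.7. The sample row in Table 1 adds no analyte. No section states a reflex test, that is, a named follow-up test set off by an abnormal AST or ALT.

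**Step 4: what is left.** Section 6.3.7 allows further evaluation, and Table 1 has an unscheduled column for adverse events. A bilirubin test may therefore be done, but the protocol states no trigger, timing or responsible person for it.

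**The case against.** The strongest reply is that section 6.3.7 is permissive and can be read in steps: the measured liver tests raise a flag, the investigator evaluates further, and a bilirubin result then decides whether the case may need reporting. On that reading bilirubin need not be a screening analyte. Other parts of the plan help. Table 1 has the unscheduled column, and its blood-sample row appears to extend to it, although the column alignment is not reliable in the extracted text. Section 6.3.6 asks that clinically relevant deterioration in non-mandated parameters be reported as an adverse event. Section 9.2 gives the monitor all AEs and SAEs, with source material on request.

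This stands as far as it goes, and it rules out several stronger readings that a reader might infer:

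- **That the rule cannot work at all.** It can, on an unscheduled bilirubin result. What the documents lack is anything that prompts the test.
- **That the monitor could never see a case.** Once a bilirubin test is done, the result can arrive as an AE or SAE or through source records. Without the test there is nothing to see.
- **That the rule fails for want of a baseline bilirubin.** The thresholds are fixed multiples of ULN, so no baseline is needed to apply them. A baseline would help in judging whether a raised value is new, but section 6.3.7 does not ask for that.
- **That a duplicate row in Table 2 was meant to be bilirubin.** The repeats suggest careless drafting, but nothing shows what was intended.

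It can also be said that Table 2 is not exhaustive: it lists no haematology, although Table 1 schedules it and the ECV formula in section 5.1 needs hematocrit. That weakens the inference from the table's silence. But hematocrit is called for elsewhere, whereas nothing outside 6.3.7 mentions bilirubin. If the local chemistry panel already reports it, the protocol should say so.

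**Conclusion.** The inconsistency is real, and it is limited to scheduled data. One of the two components of the Hy's Law criterion is in none of the 21 entries of Table 2 and is ordered nowhere else, so no scheduled draw can establish that a subject meets the criterion. Detection rests on an unscheduled test that is allowed but not triggered.

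The documents give no expected rate of liver events, so the number of cases that might be missed cannot be estimated, and none is claimed. Sections 6.9 and 9.2 describe the drug's safety profile as established, which bears on how likely a case is but does not close the gap. No efficacy endpoint, sample size or stated figure is affected.

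The conclusion assumes that Table 2 as extracted is complete. It shows no redaction and its chemistry rows are filled. It also assumes that no laboratory manual outside these documents adds bilirubin. The point is worth correcting because a written safety criterion should be answerable from the data the protocol plans to collect, and the correction is small.

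**What to change.** Reconcile sections 5.2.1 and 6.3.7 so that the measured variables match the stated criterion. The simplest way is to list total bilirubin in Table 2 at the existing AST and ALT draws. The timing sentence in 5.2.1 would then cover it with no further edit, since any variable not named there is six-monthly. It would also enter the laboratory values in the monitor's quarterly report without a separate instruction. If the sponsor and the investigator intend bilirubin to be obtained in another way, the protocol should state that. The criterion itself and any clinical response to it are theirs to settle. The repeated total cholesterol and potassium rows can be tidied in the same edit.

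The cost is one analyte on chemistry samples already being drawn, plus an amendment with IRB approval under section 10.5. The benefit is limited to draws still to come. Version 8.0 is dated July 2022, while section 9.3 gives a study period ending in March 2021, so few draws may remain in the initial 60 subjects; the documents do not say how many. The change would also serve any further enrolment that followed the sample-size re-estimation described in section 8.2. For subjects already followed, the report should state that total bilirubin was not among the protocol's scheduled variables, so that an absence of Hy's Law cases is not read as a tested finding.

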### **6.3.8 Urinary Tract Infections (UTI)**

All enrolled patients will be counseled at every clinical visit for risk of UTI and genital mycotic infection. Adequate hydration, frequent visits to the bathroom and appropriate perineal hygiene (washing with water or wipes) will be recommended.

All SAEs will be reported, whether or not considered causally related to the investigational product, or to the study procedure(s).

If any SAE occurs in the course of the study, then Investigators or other site personnel inform the appropriate funding agent, AstraZeneca, representatives within one day i.e., immediately but **no later than 24 hours** of when he or she becomes aware of it.

The Investigator will ensure that all the necessary information is provided to the database **within 1 calendar day** of initial receipt for fatal and life threatening events **and within 5 calendar days** of initial receipt for all other SAEs.

For fatal or life-threatening adverse events where important or relevant information is missing, active follow-up is undertaken immediately. Investigators or other site personnel inform funding agent, AstraZeneca, representatives of any follow-up information on a previously reported SAE within one calendar day i.e., immediately but **no later than 24 hours** of when he or she becomes aware of it.

## **6.5. Reporting of serious adverse events**

The PI must inform the FDA, via a MedWatch form, of any serious or unexpected adverse events that occur in accordance with the reporting obligations of 21 CFR 312.32, and will concurrently forward all such reports to AstraZeneca. A copy of the MedWatch report must be emailed to AstraZeneca (TCS vendor) at the time the event is reported to the FDA. It is the responsibility of the PI to compile all necessary information and ensure that the FDA receives a report according to the FDA reporting requirement timelines and to ensure that these reports are also submitted to AstraZeneca at the same time.

- \* **PI** must also indicate, either in the SAE report or the cover page, the **causality** of events **in relation to all study medications**, as determined by the principal investigator.

- \* *Send SAE report and accompanying cover page by way of email to AstraZeneca's designated mailbox:* [contact]
- If a non-serious AE becomes serious, this and other relevant follow-up information must also be provided to AstraZeneca and the FDA.

Serious adverse events that do not require expedited reporting to the Regulatory Authority/IRB/IEC still need to be reported to AstraZeneca . In the case of blinded trials, AstraZeneca will request that the Investigator either provide a copy of the randomization code/ code break information or unblind those SAEs (because of a critical patient safety concern related to that SAE), which require expedited reporting.

## **6.6. Overdose**

An overdose is defined as a patient receiving a dose of IP in excess of that specified in the Investigator's Brochure, unless otherwise specified in this protocol.

If an overdose on the study drug occurs in the course of the study, then the Investigator is required to inform AstraZeneca Patient Safety within 24 hours of the knowledge of the event using the designated safety mailbox

If the overdose results in an AE, the AE must also be recorded as an AE. Overdose does not automatically make an AE serious, but if the consequences of the overdose are serious, for example death or hospitalization, the event is serious and must be recorded and reported as an SAE

For overdoses associated with a SAE, the standard reporting timelines apply, see Section 0. For other overdoses, reporting must occur within 30 days.

The investigator will use clinical judgment to treat any overdose

## **6.7. Pregnancy**

All pregnancies and outcomes of pregnancy should be reported to UW HSD and the funding agent, AstraZeneca,.

### **6.7.1. Maternal exposure**

Women of childbearing potential are not allowed to be included in this study. Should a pregnancy still occur, the investigational product should be discontinued immediately and the pregnancy reported to the UW HSD and the funding agent, AstraZeneca,.

Pregnancy itself is not regarded as an adverse event unless there is a suspicion that the investigational product under study may have interfered with the effectiveness of a contraceptive medication. Congenital abnormalities/birth defects and spontaneous miscarriages should be reported and handled as SAEs. Elective abortions without

complications should not be handled as AEs. The outcome of all pregnancies (spontaneous miscarriage, elective termination, ectopic pregnancy, normal birth or congenital abnormality) should be followed up and documented even if the subject was discontinued from the study.

If any pregnancy occurs <<in the course of the study>>, then the Investigator or other site personnel informs the appropriate AstraZeneca representatives within 1 day i.e., immediately but **no later than 24 hours** of when he or she becomes aware of it.

The Investigator will ensure that all relevant information is provided to AstraZeneca Patient Safety within 1 or 5 calendar days for SAEs (see Section 0) and within 30 days for all other pregnancies.

The same timelines apply when outcome information is available.

